5.2 SAFETY PARAMETERS AND DEFINITIONS

Safety assessments will consist of monitoring and recording adverse events, including serious adverse events and adverse events of special interest, performing protocol-specified safety laboratory assessments, measuring protocol-specified vital signs, and conducting other protocol-specified tests that are deemed critical to the safety evaluation of the study.

Certain types of events require immediate reporting to the Sponsor, as outlined in Section 5.4.

5.2.1 Adverse Events

According to the ICH guideline for Good Clinical Practice, an adverse event is any untoward medical occurrence in a clinical investigation subject administered a pharmaceutical product, regardless of causal attribution. An adverse event can therefore be any of the following:

- Any unfavorable and unintended sign (including an abnormal laboratory finding), symptom, or disease temporally associated with the use of a medicinal product, whether or not considered related to the medicinal product
- Any new disease or exacerbation of an existing disease (a worsening in the character, frequency, or severity of a known condition), except as described in Section 5.3.5.9

- Recurrence of an intermittent medical condition (e.g., headache) not present at baseline
- Any deterioration in a laboratory value or other clinical test (e.g., ECG, X-ray) that is associated with symptoms or leads to a change in study treatment or concomitant treatment or discontinuation from study drug
- Adverse events that are related to a protocol-mandated intervention, including those that occur prior to assignment of study treatment (e.g., screening invasive procedures such as biopsies)

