5.2.2 Serious Adverse Events (Immediately Reportable to the Sponsor)

A serious adverse event is any adverse event that meets any of the following criteria:

- Is fatal (i.e., the adverse event actually causes or leads to death)
- Is life threatening (i.e., the adverse event, in the view of the investigator, places the patient at immediate risk of death)

This does not include any adverse event that had it occurred in a more severe form or was allowed to continue might have caused death.

- Requires or prolongs inpatient hospitalization (see Section 5.3.5.11)
- Results in persistent or significant disability/incapacity (i.e., the adverse event results in substantial disruption of the patient's ability to conduct normal life functions)
- Is a congenital anomaly/birth defect in a neonate/infant born to a mother exposed to study drug
- Is a significant medical event in the investigator's judgment (e.g., may jeopardize the patient or may require medical/surgical intervention to prevent one of the outcomes listed above)

The terms "severe" and "serious" are not synonymous. Severity refers to the intensity of an adverse event (e.g., rated as mild, moderate, or severe, or according to the National Cancer Institute [NCI] CTCAE); see Section 5.3.3); the event itself may be of relatively minor medical significance (such as severe headache without any further findings).

Severity and seriousness need to be independently assessed for each adverse event recorded on the eCRF.

Serious adverse events are required to be reported by the investigator to the Sponsor immediately (i.e., no more than 24 hours after learning of the event; see Section 5.4.2 for reporting instructions).

The exception to this definition of a serious adverse event is in the rare event that a patient is hospitalized following an MS relapse, as long as the reason for hospitalization is to receive standard treatment with IV methylprednisolone. The rationale for this

exception is that some countries and/or clinical sites routinely hospitalize patients who require administration of methylprednisolone in the event of an MS relapse. Thus, the serious adverse event criteria for “hospitalization” would be met on the basis of local practice and would not reflect the seriousness of the event.

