5.3.5.9 Preexisting Medical Conditions

A preexisting medical condition is one that is present at the screening visit for this study. Such conditions should be recorded on the General Medical History and Baseline Conditions eCRF.

A preexisting medical condition should be recorded as an adverse event only if the frequency, severity, or character of the condition worsens during the study. When recording such events on the Adverse Event eCRF, it is important to convey the concept that the preexisting condition has changed by including applicable descriptors (e.g., "more frequent headaches").

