6.5.1 Adverse Events

Verbatim descriptions of treatment-emergent adverse events will be mapped to thesaurus terms. Adverse events will be tabulated by body system and treatment group. Adverse events will also be summarized by maximum intensity for each treatment group (Groups A and B). Separate summaries will be provided for serious adverse events, treatment-related adverse events, and adverse events leading to study withdrawal.

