Appendix 1 Schedule of Assessments: Table A (cont.)

	Group A (A1 and A2)												
	Screening ¹	Immunization Study Period						OOE ^{2,3}			WD from Treatment	Unscheduled ⁴	Delayed Dosing ⁵
Study Day (unless noted) (Window)	-28 to -1	1 (BL)¹	15 (±2 d)	85 (±4 d)	112 (±4 d)	140 (±4 d)	169²	169²	q22w (±4 d) (-2 w prior to q24 w)	q24 w³ (±2 w)			
Week	-4 to -1	1	2	12	16	20	24	24	q22 w³	q24 w³			
MRI (once annually [±4 w]) ¹¹	x										x		
Adverse events/MS relapse	Only SAEs ¹²	x	x	x	x	x	x	x	x	x	x	x	x
Telephone interview				Every 4 weeks ¹³									
Concomitant treatments		x	x	x	x	x	x	x	x	x	x	x	x
Pregnancy test ¹⁴	x	x	x	x	x	x	x	x		x	x	x	x
ADA ¹⁵		x				x	x	x	x	x	x		
PK sampling ¹⁶		x	x	x	x	x	x	x		x	x		
FSH ¹⁷	x												
Hepatitis screening ¹⁸	x												
HBV DNA monitoring ¹⁹		x		x			x	x	x		x		
RPR	x												

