Appendix 1 Schedule of Assessments: Table B (cont.)

Group B														
	Screening ¹	Immunization Study Period				OOE ^{2,3}						WD from Treatment ⁴	Unscheduled ⁴	Delayed Dosing ⁵
Study Day (Unless Noted) Window	-28 to -1	1	28 (±4 d)	56 (±4 d)	84¹ (±4 d)	84¹ (±4 d)	98 (±2 d)	238 (±4 d)	252 (±2 d)	q22w (±4 d) (-2 w prior to q24 w)	q24 w³ (±2 w)			
Week	-4 to -1	—	4	8	12	12	14	34	36	q22 w³	q24 w³			
Weight ⁹	x					x			x		x	x		
EDSS ¹⁰		x												
MRI (once annually [±4 w]) ¹¹	x										x			
Adverse events	Only SAEs ¹²	x	x	x	x	x	x	x	x	x	x	x	x	x
Telephone interview						Every 4 weeks ¹³								
Concomitant treatments		x	x	x	x	x	x	x	x	x	x	x	x	x
Pregnancy test ¹⁴	x	x	x	x	x	x	x		x		x	x	x	x
ADA ¹⁵						x	x	x	x	x	x	x		
PK samples ¹⁶						x	x		x		x	x		
FSH ¹⁷	x													
Hepatitis screening ¹⁸	x													

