4.6.2.1 Adverse Events during the ISP

Adverse events will be defined as all adverse events, except non-serious MS relapses, but including infusion-related reactions (IRRs) and serious MS relapses. Therefore, those adverse events recorded on the “adverse event” and “infusion-related reaction (IRR)” CRF pages will be included.

For each adverse event recorded, the term entered by the investigator describing the event (the “reported term”) will be assigned a standardized term (the “preferred term”) based on the MedDRA WHO dictionary of terms. All analyses of adverse event data will be performed using the PTs unless otherwise specified.

All adverse events will be mapped to PTs and superclass terms and included in a data listing (a separate listing showing relapse information will also be presented). For all summary tables, the adverse events will be sorted by SOC (in decreasing order of overall incidence) and then by PT (in decreasing order of overall incidence). An adverse event profile summary table will be presented to provide an overview of adverse events reported in the ISP. Additionally, the most frequent adverse events ($\geq 5\%$ in any treatment group) will be presented by PT.

Summaries of adverse events will be generated by summarizing the incidence of treatment-emergent adverse events only. Treatment-emergent events are defined as those adverse events with observed or imputed onset date on or after the start date of study treatment (ocrelizumab or any vaccinations). Only where the most extreme intensity is greater than the initial intensity will events with an onset date prior to the start of study treatment (and with an end date on or after the start of study treatment) be considered treatment-emergent. An adverse event with a completely missing, non-imputed start date will be assumed to be treatment-emergent unless the adverse event has a complete non-imputed end date that is prior to start of study treatment.

Adverse events will be assigned to a dose if the adverse event onset date is on or after the date of the first infusion of that dose but before the first infusion of the next treatment dose. Adverse events that start prior to the first dose and worsen during treatment (i.e., treatment-emergent) will be assigned to the first treatment dose.

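### Non-serious MS relapses are left out of every SAP adverse event table and only listed, and neither document has a relapse outcome or a post-vaccination relapse summary to make up for it

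*Protocol*

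**What the plan says.** **Protocol.** Section 5.2.1 includes among adverse events "Any new disease or exacerbation of an existing disease (a worsening in the character, frequency, or severity of a known condition". The sentence goes on with a qualification: "or severity of a known condition), except as described in Section 5.3.5.9". That section reads: "A preexisting medical condition should be recorded as an adverse event only if the frequency, severity, or character of the condition worsens during the study".

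Section 5.2.2 deals with relapse under seriousness: "The exception to this definition of a serious adverse event is in the rare event that a patient is hospitalized following an MS relapse", provided the stay was for standard IV methylprednisolone. A stay for any other reason, or a prolonged one, makes the relapse serious. Section 5.3.1 names the adverse event page for new or worsening neurological symptoms that are not attributed to MS.

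For analysis, section 6.5.1 says: "Adverse events will be tabulated by body system and treatment group". It makes no exception for relapse.

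**SAP.** Section 4.6.2.1 says: "Adverse events will be defined as all adverse events, except non-serious MS relapses, but including infusion-related reactions (IRRs) and serious MS relapses". It provides a separate listing of relapse information and another of serious relapses. It repeats the exclusion for the registry table of non-serious events. Sections 4.6.2.2 and 4.6.2.3 carry the same approach to the extension and to all periods combined.

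**Schedules (protocol Appendix 1).** The Table A row for Group A reads "Adverse events/MS relapse". The matching Table B row for Group B reads "Adverse events".

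**The concern.** Leaving non-serious relapses out of adverse event tables costs little in a trial where relapse is an efficacy endpoint, because the events are then counted elsewhere. Here they are not. None of the primary, secondary, immunophenotyping or safety outcomes in protocol 3.4 or SAP 2.2 names relapse.

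The safety outcome in protocol 3.4.4 covers adverse events associated with ocrelizumab and with the study immunizations, and protocol 1.2 says the trial will give guidance on the safety of vaccinating these patients. For people with MS, relapse is the disease-specific event a reader will look for. Relapses may also be treated with systemic corticosteroids during the immunization period (protocol 4.6.3), so relapse counts by group would help in reading the antibody results.

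Under the present rule the report would give serious relapses in tables and leave the reader to count the rest from a listing, with no denominator in follow-up time.

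**Working it through.** The plan states no figure on this point, so there is none to reproduce. The check is first textual, then a calculation of size.

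**1. Are relapses adverse events under the protocol?**
- For: exacerbation of an existing disease is named in 5.2.1, and the 5.3.5.9 exception still requires recording when a condition worsens. Section 5.2.2 exempts some hospitalized relapses from seriousness, which is needed only if a relapse is an adverse event to begin with. The SAP's own wording takes relapses out of the set of all adverse events.
- Against: 5.3.1 names the adverse event page only for symptoms not attributed to MS.
- Result: relapses are treated as adverse events, but where an ordinary relapse is recorded is not settled.

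**2. What output covers them?**

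| Event | By-group table | By-group listing |
|---|---|---|
| Serious relapse | Yes (SAP 4.6.2.1, AE and SAE tables) | Yes |
| Non-serious relapse | None | Yes (SAP 4.6.2.1; ordering by group in SAP section 4) |
| Any relapse after first vaccination | None | Not separated |

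A hospitalized relapse falls in the second row if the stay was for standard IV methylprednisolone and no other seriousness criterion applies.

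**3. Is the departure flagged?** No. SAP 4.6.4.1 shows that the SAP can do so: it states and justifies dropping a laboratory listing that it attributes to protocol 6.5.2. Nothing similar accompanies the relapse exclusion.

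**4. Follow-up windows (protocol 3.1).**
- Group A: vaccination starts Day 85 and the period ends Day 169. After first vaccination: 169 − 85 = 84 days. Whole period: 169 − 1 = 168 days.
- Group B: vaccination starts Day 1 and the period ends Day 84: 84 − 1 = 83 days.

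SAP 4.6.2.1 starts treatment emergence at ocrelizumab or any vaccination, so Group A tables include 84 days before any vaccine.

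**5. Expected relapses after first vaccination.** Inputs: about 100 patients at 2:1 (protocol 6.1), taken as 67 and 33; t = 84/365.25 = 0.230 years, used for both groups. The relapse rate r is an assumption, equal in both groups, shown over 0.1 to 0.5 per patient-year.
- Expected relapses = n × r × t.
- Probability of at least one relapse: p = 1 − exp(−r × t).
- 95% half-width for the difference in p = 1.96 × √[p(1 − p)(1/67 + 1/33)].

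| r | Group A | Group B | p | Half-width |
|---|---|---|---|---|
| 0.1 | 1.5 | 0.8 | 0.023 | 0.062 |
| 0.3 | 4.6 | 2.3 | 0.067 | 0.104 |
| 0.5 | 7.7 | 3.8 | 0.109 | 0.130 |

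If the rate were 0.3 in Group B and 0.6 in Group A (p = 0.067 and 0.129), the power to detect the difference at two-sided 5% would be about 13%.

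**6. Why the window matters.** Suppose 0.3 per year in Group B and a rate 46% lower in Group A, borrowing the relative reduction in protocol 1.1.3.1. Over the whole period the expected relapses per patient are:
- Group A: 0.3 × 0.54 × 168/365.25 = 0.075
- Group B: 0.3 × 83/365.25 = 0.068

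A rate ratio of 0.54 then shows up as 7.5 against 6.8 relapses per 100 patients. A whole-period count without patient-years would hide it.

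**The case against.** The case for leaving the plan alone is that the exclusion is stated openly, that all relapses are listed by group, that the safety objective promises only additional safety data on ocrelizumab, and that so few events cannot support a comparison. The last point stands: the table would be descriptive. Both groups are vaccinated, so an A-versus-B contrast cannot separate a vaccine effect from an ocrelizumab effect.

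Four stronger readings are tempting, and the documents do not support them.
- *Relapse is never compared between groups.* Serious relapses remain in the AE and SAE tables by group, and counts of the others could be taken by hand from the listing.
- *The SAP breaks a clear protocol rule.* The 5.2.1 definition carries the 5.3.5.9 exception, and 5.3.1 points elsewhere for MS-related symptoms. It is an unflagged difference from 6.5.1 resting on an ambiguous recording rule.
- *The exclusion understates adverse events unevenly by arm.* SAP incidence is per patient, not per patient-year. On the figures in step 6 the two groups lose nearly the same share over the whole period, and Group A slightly more.
- *Relapses are collected only in Group A.* Table B's adverse event row is marked at every visit after screening. Relapse treatment (4.6.3) and unscheduled visits (4.7.3, 4.7.6) apply to both groups, and Group B has telephone interviews from Week 5. The differing label is a risk to equal ascertainment and no more than that.

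**Conclusion.** The point holds as a reporting gap of moderate size. Non-serious MS relapses are excluded from every adverse event table, the SAP does not flag this against protocol 6.5.1, and no relapse outcome in either document fills the gap. No relapse summary for the post-vaccination window is planned. The unequal row labels in Tables A and B add a smaller risk of unequal ascertainment.

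The events at issue are few: about 1.5 to 7.7 in Group A and 0.8 to 3.8 in Group B after first vaccination, serious and non-serious together. That rests on 67 and 33 patients, full follow-up, equal rates in the two groups and an assumed 0.1 to 0.5 relapses per patient-year. The share that would be non-serious is not known from the documents.

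The comparison is with the protocol version supplied. The SAP still describes a B-cell monitoring period that this version has dropped, so it was written against different protocol text, and 6.5.1 may have read differently then.

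**What to change.** 1. In SAP 4.6.2.1, add one descriptive table by group of all MS relapses, serious and non-serious: patients with at least one relapse, number of relapses, patient-years and rate. The main window should run from first vaccination to the end of the immunization period (about 84 days in Group A, 83 in Group B). Show the whole-period result per patient-year as well, because follow-up there is 168 against 83 days.
2. Add a row for any adverse event including relapses to the adverse event profile table, and state in the SAP that the other tables depart from protocol 6.5.1 and why.
3. Give the adverse event rows of Tables A and B the same label, and reconcile protocol 5.2.1 and 5.3.1 on which form a relapse is recorded. Protocol 1.1.4 already reports results from the immunization period, so these wording changes help later periods only. For the immunization period, report whether both groups used the same relapse form.

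The cost is one extra table and one extra row from data already needed for the relapse listing, plus small text corrections. The downside is a table with few events and wide intervals, which should be labelled descriptive and not read as evidence about a vaccine effect.

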5.2.2 Serious Adverse Events (Immediately Reportable to the Sponsor)

A serious adverse event is any adverse event that meets any of the following criteria:

- Is fatal (i.e., the adverse event actually causes or leads to death)
- Is life threatening (i.e., the adverse event, in the view of the investigator, places the patient at immediate risk of death)

This does not include any adverse event that had it occurred in a more severe form or was allowed to continue might have caused death.

- Requires or prolongs inpatient hospitalization (see Section 5.3.5.11)
- Results in persistent or significant disability/incapacity (i.e., the adverse event results in substantial disruption of the patient's ability to conduct normal life functions)
- Is a congenital anomaly/birth defect in a neonate/infant born to a mother exposed to study drug
- Is a significant medical event in the investigator's judgment (e.g., may jeopardize the patient or may require medical/surgical intervention to prevent one of the outcomes listed above)

The terms "severe" and "serious" are not synonymous. Severity refers to the intensity of an adverse event (e.g., rated as mild, moderate, or severe, or according to the National Cancer Institute [NCI] CTCAE); see Section 5.3.3); the event itself may be of relatively minor medical significance (such as severe headache without any further findings).

Severity and seriousness need to be independently assessed for each adverse event recorded on the eCRF.

Serious adverse events are required to be reported by the investigator to the Sponsor immediately (i.e., no more than 24 hours after learning of the event; see Section 5.4.2 for reporting instructions).

The exception to this definition of a serious adverse event is in the rare event that a patient is hospitalized following an MS relapse, as long as the reason for hospitalization is to receive standard treatment with IV methylprednisolone. The rationale for this

exception is that some countries and/or clinical sites routinely hospitalize patients who require administration of methylprednisolone in the event of an MS relapse. Thus, the serious adverse event criteria for “hospitalization” would be met on the basis of local practice and would not reflect the seriousness of the event.

When the MS relapse results in hospitalization for any reason other than for routine treatment of the relapse (such as for a treatment course beyond the standard treatment described in Section 4.6.3) or when hospitalization is prolonged, the MS relapse should be considered a serious adverse event.

5.2.3 Adverse Events of Special Interest (Immediately Reportable to the Sponsor)

Adverse events of special interest are required to be reported by the investigator to the Sponsor immediately (i.e., no more than 24 hours after learning of the event; see Section 5.4.2 for reporting instructions). Adverse events of special interest for this study include the following:

- Cases of potential drug-induced liver injury that include an elevated ALT or AST in combination with either an elevated bilirubin or clinical jaundice, as defined by Hy's law (see Section 5.3.5.7)
- Suspected transmission of an infectious agent by the study drug, as defined below

Any organism, virus, or infectious particle (e.g., prion protein transmitting transmissible spongiform encephalopathy), pathogenic or non-pathogenic, is considered an infectious agent. A transmission of an infectious agent may be suspected from clinical symptoms or laboratory findings that indicate an infection in a patient exposed to a medicinal product. This term applies only when a contamination of the study drug is suspected.

5.3 METHODS AND TIMING FOR CAPTURING AND ASSESSING SAFETY PARAMETERS

The investigator is responsible for ensuring that all adverse events (see Section 5.2.1 for definition) are recorded on the Adverse Event eCRF and reported to the Sponsor in accordance with instructions provided in this section and in Section 5.4–5.6.

For each adverse event recorded on the Adverse Event eCRF, the investigator will make an assessment of seriousness (see Section 5.2.2 for seriousness criteria), severity (see Section 5.3.3), and causality (see Section 5.3.4).

5.3.1 Adverse Event Reporting Period

Investigators will seek information on adverse events at each patient contact. All adverse events, whether reported by the patient or noted by study personnel, will be recorded in the patient's medical record and on the Adverse Event eCRF.

New or worsening neurological symptoms not considered MS-related should be recorded on an adverse event page and the monitor should be informed.

After informed consent has been obtained **but prior to initiation of study treatments**, only serious adverse events caused by a protocol-mandated intervention (e.g., invasive procedures such as biopsies, discontinuation of medications) should be reported (see Section [5.4.2](#) for instructions for reporting serious adverse events).

After initiation of study treatments, all adverse events will be reported until Week 48 of the SFU Period. After this period, the investigator should report any serious adverse events that are believed to be related to prior study drug treatment (see Section [5.6](#)).

